11.3. Eliciting Adverse Event Information

At every study visit, patients must be asked a standard, non-directed question, such as, “How have you been feeling since your last visit?” to elicit any medically related changes in their well-being. They may also be asked if they have been hospitalized, had any accidents, used any new medications, or changed concomitant medication regimens (including prescription drugs, over-the-counter medications, vitamins, herbal products, and minerals). Responses must be documented in the source documents.

In addition to patient observations, AEs must be documented for any clinically significant diagnosis resulting from abnormal laboratory test values, physical examination findings, or ECG abnormalities, or from other documents that are relevant to patient safety.

11.4. Assessment of Causality

The investigator must use the following classifications and criteria to characterize the relationship or association of the study drug in causing or contributing to the AE:

Not Related: This relationship suggests that there is no association between the study drug and the reported event.

Unlikely Related: This relationship suggests that the temporal sequence of the event with study drug administration makes a causal relationship improbable and/or other factors also provide plausible explanations.

Possibly Related: This relationship suggests that treatment with the study drug caused or contributed to the AE. That is, the event follows a reasonable temporal sequence from the time of study drug administration, and/or, follows a known response pattern to the study drug, but could have been produced by other factors.

Probably Related: This relationship suggests that a reasonable temporal sequence of the event with study drug administration exists and, based upon the known pharmacological action of the drug, known or previously reported adverse reactions to the drug or class of drugs, or judgment based on the investigator's clinical experience, the association of the event with study drug administration seems likely.

Definitely Related: This relationship suggests that a definite causal relationship exists between the drug administration and the AE, and other conditions (*e.g.*, concurrent illness, progression/expression of disease state, or concurrent medication reaction) do not appear to explain the event.

11.5. Assessment of Severity

The investigator will grade the severity of the AEs as mild, moderate, or severe using the following definitions:

Mild: Symptoms causing no or minimal interference with usual social and functional activities

Moderate: Symptoms causing greater than minimal interference with usual social and functional activities

Severe: Symptoms causing inability to perform usual social and functional activities

11.6. Recording Adverse Events

All conditions present prior to the administration of the first dose of study drug (Day 1) should be documented as medical history. After the first dose, documentation of adverse events (AEs) shall continue until 28 days following administration of the final dose of study medication, regardless of the relationship of the AE to study drug. Information to be collected includes type of event, date of onset, date of resolution, investigator-specified assessment of severity and relationship to study drug, seriousness, as well as any action taken.

While an AE is ongoing, changes in the severity (*e.g.*, worsening and improving) should be noted in the source documents, but when documenting the AE, only the total duration and

greatest severity should be recorded in the eCRF. AEs characterized as intermittent require documentation of onset and duration.

All drug-related (possibly, probably, or definitely related, see [Section 11.4](#)) AEs and abnormal laboratory test results reported or observed during the study must be followed to resolution (either return to baseline or within normal limits). All other AEs will be followed through the final visit indicated in [Table 3](#), as appropriate.

AEs resulting from concurrent illnesses, reactions to concurrent illnesses, reactions to concurrent medications, or progression of disease states must also be reported. Preexisting conditions (present before the start of the AE collection period) are considered concurrent medical conditions and should NOT be recorded as AEs. However, if the patient experiences a worsening or complication of such a concurrent condition, the worsening or complication should be recorded as an AE. Investigators should ensure that the AE term recorded captures the change in the condition (*e.g.*, “worsening of...”). Any improvement in condition should be documented per [Section 9.10.12](#).

[figure not shown]
Each AE should be recorded to represent a single diagnosis. Accompanying signs (including abnormal laboratory test values or ECG findings) or symptoms should NOT be recorded as additional AEs. If a diagnosis is unknown, sign(s) or symptom(s) should be recorded as an AE(s). Changes in laboratory test values or ECG parameters are only considered AEs if they are judged to be clinically significant (*i.e.*, if some action or intervention is required or if the investigator judges the change to be beyond the range of normal physiological fluctuation). If abnormal laboratory test values or ECG findings are the result of pathology for which there is an overall diagnosis (*e.g.*, increased creatinine levels in renal failure), only the diagnosis should be reported as an AE.

Elective procedures (surgeries or therapies) that were scheduled prior to the start of AE collection are not considered AEs. These elective procedures should not be recorded as AEs, but should be documented in the patient’s source documents as elective (*e.g.*, elective periodontal surgery). However, if a pre-planned procedure is performed early (*e.g.*, as an emergency) because of a worsening of the preexisting condition, the worsening of the condition should be captured as an AE.

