7. INVESTIGATIONAL PLAN

7.1. Overall Study Design

This double-blind, randomized, placebo-controlled trial will study the safety, tolerability, and efficacy of bardoxolone methyl in qualified patients with WHO Group I CTD-PAH.

Qualified patients will be randomized 1:1 to either bardoxolone methyl or placebo to be administered once daily for 24 weeks. Patients randomized to placebo will remain on placebo throughout the study and undergo sham titration. Patients randomized to bardoxolone methyl will start at 5 mg and will dose-escalate to 10 mg at Week 4, unless contraindicated clinically. Dose de-escalation is permitted during the study if indicated clinically. Please refer to [Section 7.3.1](#) for additional details on dose escalation and dose de-escalation.

All patients in the study will follow the same visit and assessment schedule. Following randomization, patients will be scheduled to be assessed in person during treatment at Weeks 1, 2, 4, 6, 8, 16, and 24 and by telephone contact on Days 3, 10, 21, 31, 38, 84, and 140. Patients will also be scheduled to be assessed at an in-person follow up visit at Week 28, four weeks after the end of treatment.

Patients who complete the study and are treatment-compliant to their assigned dose will be eligible for a separate open-label extension study.

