8.4.1. Patient Discontinuation Criteria

Discontinuation refers to a patient's stopping administration of study drug. Reasons for study drug discontinuation may include the following:

- Confirmed clinical worsening event
- Occurrence of an AE or change in medical status that leads the investigator to be concerned about the patient's welfare
- Administrative reasons (*e.g.*, inability to continue)
- Sponsor termination of the study
- Voluntary withdrawal
- Females who become pregnant during the study
- Investigator unblinding

Patients must discontinue study drug if any of the following occur.

- ALT or AST > 8X ULN;
- ALT or AST > 5X ULN for 14 days;
- ALT or AST > 3X ULN and (total bilirubin > 2X ULN or INR > 1.5);
- ALT or AST > 3X ULN with the appearance of fatigue, nausea, vomiting, right upper quadrant pain or tenderness, fever, rash, and/or eosinophilia (> 5%);

Patients who are discontinued from study drug should still continue in the study, completing all study visits and undergo all scheduled study assessments, if possible.

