11.2. Adverse and Serious Adverse Events

11.2.1. Definition of Adverse Events

11.2.1.1. Adverse Event

An adverse event (AE) is defined as any untoward medical occurrence in a patient regardless of its causal relationship to study drug. An AE can be any unfavorable and unintended sign (including any clinically significant abnormal laboratory test result), symptom, or disease temporally associated with the use of the study drug, whether or not it is considered to be study-drug related. Included in this definition are any newly-occurring events or previous condition that has increased in severity or frequency since the administration of study drug.

All AEs that are observed or reported by the patient during the study (from time of administration of the first dose at the Day 1 visit until the final visit indicated in [Table 3](#) must be reported, regardless of their relationship to study drug or their clinical significance.

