11.2.1.2. Serious Adverse Event

A serious adverse event (SAE) is any AE occurring at any dose and regardless of causality that:

- Results in death;
- Is life-threatening;
- Requires inpatient hospitalization or prolongation of existing hospitalization;
- Results in persistent or significant incapacity or substantial disruption of the ability to conduct normal life functions;
- Is a congenital anomaly or birth defect in an offspring of a patient taking study drug;
- Is an important medical event.

The term "life-threatening" refers to an event in which the patient was at immediate risk of death at the time of the event. It does not refer to an event that hypothetically might have caused death if it were more severe.

Important medical events are those that may not meet any of the criteria defined above; however, they may be considered serious when, based upon appropriate medical judgment, they may

jeopardize the patient and may require medical or surgical intervention to prevent one of the other outcomes listed in the SAE definition.

Pregnancy is not considered an AE; however, information will be collected for any pregnancies that occur during the study (from the time of the first dose of study drug until the final visit indicated in [Table 3](#), as appropriate). Certain pregnancy outcomes will require submission as an SAE (See [Section 9.8](#)).

The investigator is responsible for reporting to Reata or designee all AEs and SAEs that are observed or reported by the patient during the study (from the time of administration of the first dose of study drug until the final visit indicated in [Table 3](#), as appropriate), regardless of their relationship to study drug or their clinical significance.

The Sponsor, or the Contract Research Organization (CRO) on the behalf of the Sponsor, must be notified immediately regarding the occurrence of any SAE that occurs after the patient is randomized and throughout the study, regardless of study drug administration, including SAEs resulting from protocol-associated procedures, as defined in relevant legislation. The procedures for reporting all SAEs, regardless of causal relationship, are as follows:

- Record the SAE on the AE eCRF and complete the “Serious Adverse Event Report” form within the electronic database.
- In the event the electronic database is not functional, a paper SAE form will be available for the reporting of SAEs.

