12.2. Adverse events and serious adverse events

Each treatment emergent AE (TEAE) will be coded using the Medical Dictionary for Regulatory Activities (MedDRA version 19.0). An AE is defined as any untoward medical occurrence in a patient regardless of its causal relationship to study treatment. A TEAE must have an onset or worsen in severity on or after the first dose of study drug and not more than 30 days after the date of the last dose of study drug. AEs with an onset greater than 30 days after the last dose of study drug, and therefore not treatment-emergent AEs (TEAEs), are classified as off-treatment AEs (OTAEs). Analyses described for TEAEs are also performed for OTAEs and tabulated separately.

A SAE is defined as an adverse event that results in death, is life-threatening, requires inpatient hospitalization or prolongation of existing hospitalization, results in persistent or significant incapacity or substantial disruption of the ability to conduct normal life functions, is a congenital anomaly or birth defect in the offspring of a patient taking the study drug, or is an important medical event. Important medical events are defined as events that may jeopardize the patient or result in medical or surgical intervention to prevent one of the outcomes listed above. The term “life-threatening” refers to an event in which the patient was at immediate risk of death at the time of the event.

Adverse events resulting from concurrent illnesses, reactions to concurrent medications, or progression of disease states will be reported. Conditions existing prior to the start of the AE collection period are considered concurrent medical conditions and are not recorded as AEs. If the patient experiences a worsening or complication of a concurrent medical condition, the worsening or complication will be recorded as an AE.

Each AE will be recorded as a single diagnosis. Accompanying signs and symptoms will not be recorded as additional AEs. Signs and symptoms will only be recorded if the diagnosis is not determined. Changes in laboratory tests values or ECG parameters will be recorded if they are determined to be clinically significant; however, abnormal test values or ECG findings will not be reported as AEs if they are the result of pathology for which there is an overall diagnosis.

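### Protocol 11.6 and 11.2 end AE recording at different times for patients who stop drug early but stay in the study, and the non-serious off-treatment AE tables depend on which one a site follows

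*Protocol*

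**What the plan says.** **Collection.** Protocol 11.6 sets the end of AE recording relative to dosing: "documentation of adverse events (AEs) shall continue until 28 days following administration of the final dose of study medication". Protocol 11.2.1.1 sets it relative to the visit schedule: AEs must be reported "from time of administration of the first dose at the Day 1 visit until the final visit indicated in" Table 3. Protocol 11.2.1.2 repeats this for AEs and SAEs together, "from the time of administration of the first dose of study drug until the final visit indicated in" Table 3. That section also has a wider rule for serious events, under which the sponsor must be told of "any SAE that occurs after the patient is randomized and throughout the study, regardless of study drug administration", with the event entered on the AE eCRF.

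**Follow-up.** Protocol 7.1 places the last contact at an "in-person follow up visit at Week 28, four weeks after the end of treatment". Table 3 dates it Day 196±3 and schedules AE collection there. Protocol 8.4.1 states: "Patients who are discontinued from study drug should still continue in the study, completing all study visits", where possible.

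**Analysis.** SAP 12.2 counts an event as treatment-emergent up to 30 days after the last dose. It classes "AEs with an onset greater than 30 days after the last dose of study drug" as off-treatment and repeats the TEAE analyses for them in separate tables. SAP 12.1 runs the safety analyses to the end of the study. Neither SAP section says which collection rule feeds these tables.

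**The concern.** The protocol gives two end points for recording a new AE and does not say which prevails. The later sentence in 11.6 on following other AEs through the final visit does not settle it, because it concerns events already recorded and not new onsets.

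The SAP tables need data that one of the rules does not collect. The off-treatment tables begin after day 30, and 11.6 stops at day 28. A sparse or empty non-serious table could be read as little happening off drug when it only shows that nobody was asked to record it. If sites differ in which section they follow, ascertainment in early stoppers also differs by site.

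**Working it through.** No sample-size or error-rate formula is involved; this is calendar arithmetic.

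**Inputs.** End-of-treatment visit Day 168±3 and final visit Day 196±3 (Protocol Table 3). Recording stop of 28 days after the final dose (Protocol 11.6) or the final visit (Protocol 11.2.1.1, 11.2.1.2). TEAE limit of 30 days after the last dose (SAP 12.2).

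**The plan's own figure.** Protocol 7.1 puts the final visit four weeks after treatment ends: 196 − 168 = 28 days, which agrees.

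**Completers.** Under 11.6, recording stops at 168 + 28 = Day 196. Under 11.2 it stops at the final visit, also Day 196, so the rules coincide at nominal timing. With both visit windows, and the last dose at the end-of-treatment visit, the interval runs from 193 − 171 = 22 to 199 − 165 = 34 days. At the nominal 28 days, neither rule reaches days 29-30 of the TEAE window.

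**Early stoppers who stay in the study.** Let L be the day of last dose, with the final visit on Day 196.

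- Stop under 11.6 = L + 28.
- Stop under 11.2 = 196.
- Difference = 168 − L.
- Off-treatment AE observation under 11.2 = max(0, 196 − L − 30).
- Off-treatment AE observation under 11.6 = max(0, 28 − 30) = 0 for every L (non-serious AEs).

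| Last dose (day) | Stop under 11.6 | Stop under 11.2 | Difference (days) | Days observed beyond day 30 under 11.2 |
|---|---|---|---|---|
| 28 | 56 | 196 | 140 | 138 |
| 45 | 73 | 196 | 123 | 121 |
| 56 | 84 | 196 | 112 | 110 |
| 112 | 140 | 196 | 56 | 54 |
| 140 | 168 | 196 | 28 | 26 |
| 168 | 196 | 196 | 0 | 0 |

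**Effect on TEAEs.** Under 11.6, 2 of the 30 post-dose days (2/30 = 6.7%) are not collected. Under 11.2 both days are covered at nominal timing if L ≤ 196 − 30 = Day 166.

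**Effect on off-treatment AEs.** Under 11.6 no non-serious onset after day 30 can enter the tables. Under 11.2, at nominal timing, a patient contributes if L ≤ 196 − 31 = Day 165. A completer at the extreme of both windows contributes at most 34 − 30 = 4 days. Under 11.2, therefore, nearly all the content comes from early stoppers who stay in the study.

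**Serious events.** The SAE rule in 11.2.1.2 runs for the whole study, on or off drug, and sends the event to the AE eCRF. Serious off-treatment events reach the tables whichever rule a site applies to other AEs.

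**The case against.** The strongest reply is that the documents lean clearly one way. Reporting to the final visit appears twice in Protocol 11.2. Table 3 schedules AE collection through Week 28, Protocol 11.3 has patients asked about AEs at every visit, and SAP 12.1 carries safety analysis to the end of the study. One sentence in 11.6 departs from this, and it fits the completer exactly, so it reads like wording written with completers in mind. That sites would actually stop at 28 days is conjecture.

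This probably describes the intent, and it limits the weight of the point. It does not remove it. Section 11.6 is the section on how AEs are recorded, its sentence is explicit, and no text ranks it below 11.2.

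The scope is also narrow, and that stands. The rules agree at nominal timing for completers. They roughly agree for patients who leave the study and return four weeks after their early termination visit. Only retained early stoppers are affected.

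Three stronger readings are tempting, and the documents do not support them:

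- A reader might infer that the whole off-treatment AE table would be empty. The SAE rule in 11.2.1.2 rules that out; only the non-serious part is exposed.
- A reader might blame 11.6 for losing days 29-30 in everyone. In a nominal completer those days fall after the last visit under either rule.
- A reader might infer a bias between arms. Protocol 5.1.3 describes transaminase rises on drug and 8.4.1 has stopping rules tied to them, so unequal stopping is possible. The documents give no stopping rates by arm, so a bias is not shown.

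**Conclusion.** The inconsistency is real and should be corrected. It is a wording conflict with limited reach: non-serious AEs, in patients who stop drug early and remain in the study, at any site that follows 11.6 as written. For such a patient the unrecorded period is 168 − L days, for example 123 days for a last dose on Day 45. If every site followed 11.6, the non-serious off-treatment AE tables would be empty by rule; if only some did, the tables would be incomplete to an unknown degree. The TEAE loss is small, at two days of 30.

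These figures assume that the patient stays until a final visit on Day 196; the ±3-day window moves the 123 days to between 120 and 126. The documents do not give the number of early stoppers, so the number of AEs affected cannot be calculated.

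**What to change.** Reconcile the sentence in Protocol 11.6 with 11.2.1.1 and 11.2.1.2, so that all AEs, serious or not, are recorded through the final study visit, and say explicitly that this includes patients who stop drug early and remain in the study. The SAP 12.2 definitions of TEAE and off-treatment AE can stay as they are. The cost is a protocol wording change and a few more AE entries at visits where AE collection is already scheduled.

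Separately, add a note to SAP 12.2 that for completers the final visit falls about 28 days after the last dose (22 to 34 with visit windows), so days 29-30 of the TEAE window are not reliably observed. This costs one sentence. No additional patient contact is needed: extending collection to a full 30 days would put a nominal completer at 168 + 30 = Day 198, after the last scheduled visit, and would add a contact for most completers for little gain.

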11.7. Reporting Serious Adverse Events

Any AE the investigator considers serious according to the previously described criteria must be reported within 24 hours from the time the site personnel first learn about the event. The eCRF system within the clinical database is the preferred method of reporting an SAE.

To report the SAE, the investigator will complete the SAE form in the clinical database and submit [REDACTED] (Refer to [Table 6](#)) within 24 hours of awareness. If the clinical database is down for any reason, the manual SAE forms should be used; however, sites are responsible for ensuring the information on the manual SAE forms is entered into the clinical database once available.

Table 6: SAE Reporting Contact InformationA rectangular box containing several lines of text that have been completely redacted with black bars. The redaction covers the entire content of the table.

For questions regarding SAE reporting, contact your study manager, monitor, [REDACTED]

Follow-Up Reports

The investigator must continue to follow the subject until the SAE has subsided or until the condition becomes chronic in nature, stabilizes (in the case of persistent impairment, or the subject dies.

Within 24 hours of receipt of new information, the SAE form should be updated within the clinical database and submitted along with any supporting documentation (e.g., subject discharge summary or autopsy reports) [REDACTED] (refer to Table 6). If the clinical database is down for any reason, the manual SAE forms should be used; however, sites are responsible for ensuring the updated information on the manual SAE forms is entered into the clinical database once available.

The Sponsor or designee will notify regulatory agencies of any fatal or life-threatening unexpected events associated with the use of the study drug as soon as possible but no later than 7 calendar days after the initial receipt of the information. Initial notification will be followed by a written report within the timeframe established by the appropriate regulatory agency. For other SAEs that do not meet the fatal or life-threatening unexpected criteria, but are reported to be associated with the use of the study drug, Reata or designee will notify the appropriate regulatory agencies in writing within the timeframe established by those regulatory agencies. Reata or designee will provide copies of any reports to regulatory agencies regarding serious and unexpected SAEs to the investigators for review and submission to their institutional review board (IRB or Ethics Committee (EC, as appropriate.

Principal investigators are responsible for informing their IRB/EC of any SAEs at their site. SAE correspondence with regulatory authorities or IRBs/ECs must be submitted to the Sponsor or designee for recording in the study file.

Note that the following adverse events which are commonly observed in this patient population will not be reported to regulatory authorities as individual expedited reports, except in unusual circumstances.

- Shortness of breath
- Lightheaded/dizzy

- Syncope
- Chest pain
- Palpitations
- Fatigue
- Edema/fluid retention
- Exertional dyspnea
- Hypoxemia

These events will be reviewed on a regular basis in aggregate and will be reported in an expedited manner if a safety signal is detected. Regular safety study updates will be reported to regulatory authorities according to local guidelines.

